11.1.4.1 Evaluation of Target Lesions

Complete Response (CR): Disappearance of all target lesions. Any pathological lymph nodes (whether target or non-target) must have reduction in short axis to <10 mm.

Partial Response (PR): At least a 30% decrease in the sum of the diameters of target lesions, taking as reference the baseline sum diameters.
Progressive Disease (PD): At least a 20% increase in the sum of the diameters of target lesions, taking as reference the smallest sum on study (this includes the baseline sum if that is the smallest on study). In addition to the relative increase of 20%, the sum must also demonstrate an absolute increase of at least 5 mm. (Note: the appearance of one or more new lesions is also considered progressions).

Stable Disease (SD): Neither sufficient shrinkage to qualify for PR nor sufficient increase to qualify for PD, taking as reference the smallest sum diameters while on study.

11.1.4.2 Evaluation of Non-Target Lesions

Complete Response (CR): Disappearance of all non-target lesions and normalization of tumor marker level. All lymph nodes must be non-pathological in size (<10 mm short axis).

Note: If tumor markers are initially above the upper normal limit, they must normalize for a patient to be considered in complete clinical response.

Non-CR/Non-PD: Persistence of one or more non-target lesion(s) and/or maintenance of tumor marker level above the normal limits.

Progressive Disease (PD): Appearance of one or more new lesions and/or *unequivocal progression* of existing non-target lesions. *Unequivocal progression* should not normally trump target lesion status. It must be representative of overall disease status change, not a single lesion increase.

Although a clear progression of "non-target" lesions only is exceptional, the opinion of the treating physician should prevail in such circumstances, and the progression status should be confirmed at a later time by the review panel (or Principal Investigator).

11.1.4.3 Evaluation of Best Overall Response

The best overall response is the best response recorded from the start of the treatment until disease progression/recurrence (taking as reference for progressive disease the smallest measurements recorded since the treatment started). The patient's best response assignment will depend on the achievement of both measurement and confirmation criteria.

Target	Non-Target	New	Overall	Best Overall Response when
Lesions	Lesions	Lesions	Response	Confirmation is Required*
CR	CR	No	CR	≥4 wks. Confirmation**
CR	Non-CR/Non-	No	PR	
	PD			
CR	Not evaluated	No	PR	>1 who Confirmation**
PR	Non-CR/Non-	No	PR	≥ 4 wks. Commutation
	PD/not			
	evaluated			
SD	Non-CR/Non-	No	SD	Desumanted at least once >4
	PD/not			vike from baseline**
	evaluated			wks. nom basenne
PD	Any	Yes or No	PD	
Any	PD***	Yes or No	PD	no prior SD, PR or CR
Any	Any	Yes	PD	
* See RECIST 1.1 manuscript for further details on what is evidence of a new lesion.				
** Only fo	** Only for non-randomized trials with response as primary endpoint.			
*** In exceptional circumstances, unequivocal progression in non-target lesions may be				
accepte	accepted as disease progression.			

For Patients with Measurable Disease (*i.e.*, Target Disease)

Note: Patients with a global deterioration of health status requiring discontinuation of treatment without objective evidence of disease progression at that time should be reported as "*symptomatic deterioration*." Every effort should be made to document the objective progression even after discontinuation of treatment.

For Patients with Evaluable (non-measurable) Disease (*i.e.*, Non-Target Disease)

Non-Target Lesions	New Lesions	Overall Response	
CR	No	CR	
Non-CR/non-PD	No	Non-CR/non-PD*	
Not all evaluated	No	not evaluated	
Unequivocal PD	Yes or No	PD	
Any	Yes	PD	
* 'Non-CR/non-PD' is preferred over 'stable disease' for non-target disease since SD is			
increasingly used as an endpoint for assessment of efficacy in some trials so to assign			
this category when no lesions can be measured is not advised.			

11.1.5 Duration of Response

Duration of overall response: The duration of overall response is measured from the time measurement criteria are met for CR or PR (whichever is first recorded) until the first date that recurrent or progressive disease is objectively documented (taking as reference for progressive disease the smallest measurements recorded since the treatment started).

The duration of overall CR is measured from the time measurement criteria are first met for CR until the first date that progressive disease is objectively documented.

Duration of stable disease: Stable disease is measured from the start of the treatment until the criteria for progression are met, taking as reference the smallest measurements recorded since the treatment started, including the baseline measurements.

12. REGULATORY REQUIREMENTS/DATA COLLECTION

Adverse event lists, guidelines, and instructions for AE reporting can be found in Section 7.0 (Adverse Events: List and Reporting Requirements).

12.1 Data Reporting

12.2 Compliance with Laws and Regulations

The study will be conducted in accordance with U.S. Food and Drug Administration (FDA) and International Conference on Harmonization (ICH) Guidelines for Good Clinical Practice (GCP), the Declaration of Helsinki, any applicable local health authority, and Institutional Review Board (IRB) requirements. The PI or designee will be responsible for obtaining continuing and not less than annual IRB re-approval throughout the duration of the study. Copies of the Investigator's annual report to the IRB and copies of the IRB continuance of approval must maintained by the appropriate participating site and the Coordinating Site (CHCO). The PI or designee is also responsible for notifying the Data and Safety Monitoring Committee (DSMC) and the participating sites IRB of record of any significant adverse events that are serious and/or unexpected, as per standard operating procedure for those entities. In addition, the DSMC will review all adverse events at routine intervals as outlined below.

12.3 Protocol Review and Amendments

This protocol, the proposed informed consent and assent forms along with any documents given to participants (e.g., drug diaries) must be submitted, reviewed and approved by a properly constituted IRB governing each study location. This process will occur following approval by the Coordinating Center IRB (COMIRB).

Any changes made to the protocol will be submitted as amendments and must be approved by the IRB that governs CHCO prior to implementation. The overall study PI and/or study coordinator will then distribute all amendments to the participating sites for submission to their local IRB. All sites must then send all approved documents to the overall study coordinator at CHCO.

12.4 Informed Consent

All participants must be provided a consent and assent form (if applicable) describing the study. All participants must be provided sufficient information to make an informed decision about their participation in this study. The formal consent of a participant, using the IRB approved consent form, must be obtained before the participant is involved in any study-related procedure. The consent form must be signed and dated by the participant or the participant's legally Protocol # 15-0659 Version Date: March 22, 2017

authorized representative, and by the person obtaining the consent. The participant must be given a copy of the signed and dated consent document. The original signed copy of the consent document must be retained in the medical record or research file.

12.5 Study Documentation

The investigator must prepare and maintain adequate and accurate source documents designed to record all observations and other data pertinent to the study for each research participant. This information enables the study to be fully documented and the study data to be subsequently verified.

12.6 DATA AND SAFETY MONITORING

The overall PI Coordinating Center (CHCO) will be responsible for monitoring the trial per the trial monitoring plan, in addition to overseeing the safety and efficacy of the trial, executing the DSM plan and complying with all reporting requirements to the local and federal authorities. This oversight will be accomplished through additional oversight from the Data and Safety Monitoring Committee (DSMC) at the University of Colorado Cancer Center (CU Cancer Center).

12.4.1. Monitoring Plan

As the lead investigator in this multi-site trial, the overall PI is responsible for organizing and conducting monthly teleconferences with all participating sites. The overall PI will also be responsible for including data from all of the participating sites within the overall trials sixmonth DSM report to the DSMC to include minutes from monthly PI teleconferences. Each participating site will be responsible for submitting the results and recommendations from the DSMC's six-month review to their local IRB of record at the time of continuing review.

Teleconferences will take place with each participating site only when there are active patients. This call will include the local investigator, local research coordinator, and overall PI and CHCO coordinator.

12.4.2 **Subject Data Monitoring:**

Monitoring and auditing of research subjects on study will be conducted remotely by the CHCO coordinator and overall study PI. Documentation that will be monitored is listed in the following section. Data will be monitored for completeness and adherence to protocol requirements.

12.7 Data and Safety Monitoring Committee (DSMC)

The DSMC is responsible for ensuring data quality and patient safety for all clinical studies at the CU Cancer Center. A summary of the DSMC's activities is as follows:

- Conduct internal audits
- Ongoing review of all serious adverse events (SAEs), unanticipated problems (UAPs) and reportable adverse events (AEs)
- Has the authority to close and/or suspend trials for safety or trial conduct issues
- May submit recommendations for corrective actions to the CU Cancer Center's Executive Committee

All SAEs, UAPs and reportable AEs are to be reported to the DSMC within 5 business days of receiving notification of the occurrence. For all sub sites, please adhere to the tables in Section 7.4 for AE reporting timelines to CHCO. Once the AE is reported to CHCO, the primary coordinator will report AEs, as required to the DSMC and IRB for review.

The overall PI will provide a DSM report to the CU Cancer Center DSMC on a six monthly basis. The DSM report will include a protocol summary; current numbers; summary of toxicity data to include specific SAEs, UAPs and AEs; any dose modifications; all protocol deviations; and protocol amendments. Results and recommendations from the review of this six month report by the DSMC will then be submitted by CHCO to all participating sites so they may submit to their IRB of record at time of continuing review.

12.8 Data Collection

Data will be collected for this study and sent to CHCO for review via email or fax. Data will be collected by the CHCO coordinator and reviewed along with the overall PI.

Form / Source Documentation (SD)	Submission Timeline
Eligiblity Checklist	Complete prior to registration with CHCO

All source documentation that is submitted with the eligibility checklist must be de-identified. The only documents that will not be de-identified are the consent/assent forms and Patient Data Sheet. All other forms and source documents submitted will be identified only by the subject number.

12.8.1 Method

Instructions for submitting data are listed in Study-Specific Data Management Plans created by CRDM SRF staff.

13. STATISTICAL CONSIDERATIONS

13.1 Study Design/Endpoints

A phase I, dose-escalation trial is proposed to determine the recommended phase II dose (RP2D) of escalating doses of eribulin in combination with standard-dose oral irinotecan. Cohorts of 3 patients per dose level are proposed using a 3+3 design [70, 71]. The following rules will be incorporated for dose escalation/de-escalation and establishing the recommended Phase II dose using the occurrence of DLT during the first cycle of therapy that is possibly, probably, or definitely attributable to study therapy.

A. Evaluate 3 patients at dose_k:

- 1. If 0 of 3 patients have DLT, then
 - i. If first cohort, increase dose to $dose_{k+1}$ and go to A.
 - ii. Otherwise, go to B.
- 2. If 1 of 3 patients has DLT, then go to B.
- 3. If more than 1 patient has DLT

- i. If lowest dose, then go to C.
- ii. Otherwise, decrease dose to $dose_{k-1}$ and go to A.
- B. Evaluate 3 additional patients at dose_k:
 - 1. If 0 or 1 of 6 patients has DLT, then increase dose to $dose_{k+1}$ and go to A.
 - 2. If 2 or more patients have DLT, then
 - i. If lowest dose, then go to C.
 - ii. Otherwise, decrease dose to $dose_{k-1}$ and go to A.
- C. Discontinue dose escalation/de-escalation.

The RP2D is defined as the highest dose level in which there is no more than 1 DLT in 6 patients. Ten additional patients will be enrolled at the RP2D level. Similar dose modifications as specified in Section 6 would be applied to these patients. Doses higher than dose level 2 will not be studied in this trial.

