5.2 Agent Administration

Treatment may be administered either in the inpatient or outpatient setting. Reported adverse events and potential risks are described in Section 7. Appropriate dose modifications are described in Section 6. No investigational or commercial agents or therapies other than those described below may be administered with the intent to treat the patient's malignancy.

Dose Escalation Schedule				
		Dose		
Dose Level	Irinotecan (mg/m ² /day)	Eribulin (mg/m²/dose)		
Level 0	90	0.8		
STARTING DOSE: Level 1	90	1.1		
Level 2	90	1.4		

There will be no intra-patient dose escalations.

Therapy Delivery Map – Cycle #		
	Patient name	DOB

DRUG	ROUTE	DOSAGE	DAYS	Observa	ations
Eribulin	IV over 2-5 min	See dose escalation scheme	1,8	a. 1 b. 1	History Physical Exam
Irinotecan	РО	90 mg/m ² /dose	1-5 (On day 1, irinotecan is given at least 15 minutes after eribulin)	c. (d. (e.)	(Ht/Wt/VS/ performance status) CMP CBC Pharmacokinetics ¹
Cefixime	PO	400 mg/day	-1 through 8		

Ht _____ Wt ____ BSA _____ Dose level = _____

Assigned Eribulin dose is $_{mg/m^2} = _{mg}$

Date	Date	Day	Eribulin	Irinotecan	Cefixime	Studies
Due	Given					
		-1 (20*)			mg	
		0 (21*)			mg	
		1	mg	mg	mg	a, b, c, d, e ¹
		2		mg	mg	
		3		mg	mg	
		4		mg	mg	$e (optional)^2$
		5		mg	mg	
		6			mg	
		7			mg	
		8	mg		mg	b, c^3 , d^4 , e^1
		15				c^{3}, d^{4}
		20			mg	
		21			mg	

¹Blood samples for pharmacokinetic testing will be obtained pre-dose, 0.25, 1, 1.5, 2, 4, and 5 hours after the administration of eribulin on day 1 and prior to day 8 dose with regularly obtained labs (see Appendix g for Pharmacokinetic Study Form). **These samples will only be collected in the first treatment cycle.**

² An optional single pharmacokinetic sample may be collected anytime between 24-96 hours if labs are being obtained at UK for other purposes.

³CMP must be drawn weekly during cycle 1, and then may be drawn only at the start of subsequent cycles ⁴CBC with differential should be drawn **twice weekly during the first cycle**, and then must be drawn at least weekly during subsequent cycles

On day 1 in which eribulin and oral irinotecan are administered concurrently, the eribulin should precede irinotecan by at least 15 minutes.

Subsequent cycles should start after day 21 as soon as the ANC \geq 1,000/µL and platelets \geq 100,000/µL, and eligibility criteria are met for renal and hepatic function (Section 3.1). This start date could vary by 3 days.

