5.6 Dose Escalating Criteria

A 3 + 3 design will be used to determine dose assignment for patients, as described in Section 13.2. Specifically, the following rules will apply for dose escalation:

- A. Evaluate 3 patients at $dose_k$:
 - 1. If 0 of 3 patients have DLT, then
 - i. If first cohort, increase dose to $dose_{k+1}$ and go to A.
 - ii. Otherwise, go to B.
 - 2. If 1 of 3 patients has DLT, then go to B.
 - 3. If more than 1 patient has DLT
 - i. If lowest dose, then go to C.
 - ii. Otherwise, decrease dose to $dose_{k-1}$ and go to A.
- B. Evaluate 3 additional patients at dose_k :
 - 1. If 0 or 1 of 6 patients has DLT, then increase dose to $dose_{k+1}$ and go to A.
 - 2. If 2 or more patients have DLT, then
 - i. If lowest dose, then go to C.
 - ii. Otherwise, decrease dose to $dose_{k-1}$ and go to A.
- C. Discontinue dose escalation/de-escalation.

Accrual will continue until the recommended phase II dose for a Phase II study (RP2D) is established and at least 6 patients have been treated at this dose. The RP2D is the highest dose level at which no more than 1 of 6 patients experiences first-cycle DLT. Doses higher than dose level 2 will not be studied in this trial. Once the RP2D is identified, an additional 10 patients will be enrolled at this dose level.

5.7 **Duration of Therapy**

In the absence of treatment delays due to adverse event(s), treatment may continue for up to 17 cycles until one of the following criteria applies:

• Disease progression

- Intercurrent illness that prevents further administration of treatment
- Unacceptable adverse event(s)
- Patient decides to withdraw from the study
- General or specific changes in the patient's condition render the patient unacceptable for further treatment in the judgment of the investigator.

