13.2 Sample Size/Accrual Rate

The primary goal of this Phase I trial is to determine the RP2D and assess safety of the combination regimen. A total of 6 -22 adolescent and young adult subjects will be accrued into the trial

It is anticipated that 0.5-1 subjects will be accrued per month so that study accrual will be completed within 36 months.

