13.5 Data Management

The study statistician and staff from the Biostatistics Shared Resource Facility (BSRF) of the Markey Cancer Center worked closely with the study investigators and the Clinical Research and Data Management (CRDM SRF) at Markey in the development of eCRFs for the study. Specifically, the statisticians attended several meetings including the Protocol Initiation Meeting (PIM) to address all statistical considerations for this protocol including incorporation of dose-escalation plans for this Phase I trial, appropriate and accurate collection of primary and secondary study endpoints and inclusion of valid values and range checks for data fields. Red Cap, managed by staff at CHCO, will be the primary database repository of clinical data from all patients enrolled into this trial. Data will be accessed by the study statistician on a regularly-scheduled basis to perform statistical programming for conduct of data quality control, data management, generation of interim reports and statistical analysis. The BSRF has developed an automated mechanism for generating a trigger for assessment of dose limiting toxicities based on the dose escalation rules in sections section 5.0 above. In collaboration with the study team, procedures will be developed for timelines for data quality control, resolution of data queries, interim reporting and final data analysis.

APPENDIX A	PERFORMANCE	STATUS CRITERIA

ECO)G Performance Status Scale	Karnofsky Performance Scale		
Grade	Descriptions	Percent	Description	
0	Normal activity. Fully active, able	100	Normal, no complaints, no evidence of disease.	
0	performance without restriction.	90	Able to carry on normal activity; minor signs or symptoms of disease.	
1	Symptoms, but ambulatory. Restricted in physically strenuous activity, but ambulatory and able	80	Normal activity with effort; some signs or symptoms of disease.	
	to carry out work of a light or sedentary nature (e.g. , light housework, office work).	70	Cares for self, unable to carry on normal activity or to do active work.	
2	In bed <50% of the time. Ambulatory and capable of all self-care, but unable to carry out	60	Requires occasional assistance, but is able to care for most of his/her needs.	
	any work activities. Up and about more than 50% of waking hours.	50	Requires considerable assistance and frequent medical care.	
2	In bed >50% of the time. Capable of only limited self-care, confined	40	Disabled, requires special care and assistance.	

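### The 3+3 steps return new patients to a level already left for toxicity and do not say whether earlier patients at a level count, which can change the RP2D

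*Combined protocol and SAP*

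**What the plan says.** Sections 5.6 and 13.1 give the same lettered steps. There are three eribulin levels (0, 1 and 2), and dosing begins at level 1 ("STARTING DOSE: Level 1", Section 5.2). Step A evaluates 3 patients. The first cohort moves up on 0 of 3 DLTs; any later cohort with 0 or 1 of 3 goes to step B, which adds 3 more. Step B.1 is "If 0 or 1 of 6 patients has DLT, then increase dose to $dose_{k+1}$ and go to A". Two or more DLTs above the lowest level lead to "Otherwise, decrease dose to $dose_{k-1}$ and go to A". Step C, the stop, is reached only by two or more DLTs at the lowest level.

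The prose says something different about stopping. Section 13.1: "The RP2D is defined as the highest dose level in which there is no more than 1 DLT in 6 patients". Section 5.6 sets a minimum number treated at the chosen level before dose finding ends: "Accrual will continue until the recommended phase II dose for a Phase II study (RP2D) is established and at least 6 patients". The expansion cohort comes next: "Once the RP2D is identified, an additional 10 patients will be enrolled at this dose level". Levels above 2 are excluded. Section 13.2 gives the size: "A total of 6 -22 adolescent and young adult subjects will be accrued into the trial". Section 13.5 reports that "The BSRF has developed an automated mechanism for generating a trigger for assessment of dose limiting toxicities based on the dose escalation rules".

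**The concern.** Three things do not fit together.

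1. **Stopping.** The only lettered exit is failure of the lowest level, so the steps never end with level 0 or level 1 chosen. Suppose level 1 shows 0/3, level 2 is left with two DLTs, and level 1 is completed with at most 1 DLT in 6. The prose says level 1 is the RP2D. Step B.1 says to treat new patients at level 2. The same conflict arises at level 0 after level 1 has failed. (B.1 at level 2 is not in question, because the cap settles it.)
2. **Counting.** On return to a level, step A asks for 3 patients and does not mention those already treated there.
3. **Sample size.** The upper total of 22 does not cover every path that the rules allow.

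These steps are the decision rule for the primary objective, and they fix the dose for the 10 expansion patients. At stake are new patients being assigned to a level already judged too toxic, and an RP2D that depends on how the rule is read.

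**Working it through.** **The plan's own range.** Minimum: level 1 fails in 3 and level 0 fails in 3, so 3 + 3 = 6 with no expansion. Maximum: two levels of 6 plus expansion, 6 + 6 + 10 = 22. Both ends of 6–22 are reproduced.

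**Paths that need no assumed rates.**
- Level 1 at 0/3, level 2 fails, and the next level-1 cohorts would show 1 and then 1 DLT. Cumulative: 1/6 after the second cohort, so level 1 passes and the third is not needed. Afresh: 1/3, then 2/6, so level 1 fails and the plan drops to level 0.
- Level 1 at 1/6 when level 2 fails. Cumulative: level 1 is the RP2D at once. Afresh: 3 or 6 more are treated there, and the level may fail.
- Cumulative totals above 22: level 1 (3), level 2 fails (3 or 6), level 1 fails on completion (3), level 0 passes (6), expansion (10). That is 3+3+3+6+10 = 25 or 3+6+3+6+10 = 28. Counted afresh, the maximum is 6+6+6+6+10 = 34.

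**How often counting matters.** Let p1 and p2 be the DLT rates at levels 1 and 2. These rates are assumptions, and the prose stop is applied throughout.
- F(p) = (1−p)^6 + 6p(1−p)^5: at most 1 DLT in 6.
- G(p) = (1−p)^3 + 3p(1−p)^2: at most 1 DLT in 3.
- Return to level 1 standing at 0/3: R0 = (1−p1)^3 × [1−F(p2)].
- Return to level 1 standing at 1/6: R1 = 3p1(1−p1)^5 × [1−F(p2)].
- Level 1 chosen, cumulative: R0·G(p1) + R1. Level 1 chosen, afresh: (R0 + R1)·F(p1).
- Difference: R0·[G(p1)−F(p1)] + R1·[1−F(p1)].

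Worked for p1 = 0.20 and p2 = 0.35: 1−F(p2) = 0.681; R0 = 0.512 × 0.681 = 0.349; R1 = 0.1966 × 0.681 = 0.134; G(p1) = 0.896; F(p1) = 0.655. The difference is 0.349 × 0.241 + 0.134 × 0.345 = 8.4% + 4.6% = 13.0%.

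| Assumed rates, levels 0/1/2 | Counting | Level 2 | Level 1 | Level 0 | None |
|---|---|---|---|---|---|
| 5/10/20% | cumulative | 59.4% | 30.5% | 9.8% | 0.3% |
| | afresh | 59.4% | 27.7% | 12.5% | 0.4% |
| 10/20/35% | cumulative | 22.6% | 44.6% | 29.0% | 3.7% |
| | afresh | 22.6% | 31.6% | 40.5% | 5.2% |
| 15/30/45% | cumulative | 8.1% | 35.1% | 44.1% | 12.7% |
| | afresh | 8.1% | 17.4% | 57.9% | 16.7% |

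The level-1 differences before rounding are 2.9, 13.0 and 17.8 points. Passing on 6 fresh patients requires at most 1 DLT in the first 3 of them, which already passes the cumulative rule. So counting afresh can only move the result down.

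**How often step B.1 conflicts with the prose.** It does so whenever the prose names level 1 or level 0, since the level above has then failed. With cumulative counts this is 30.5 + 9.8 = 40.3%, 44.6 + 29.0 = 73.6% and 35.1 + 44.1 = 79.2% of trials.

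**Enrolment above 22.** Cumulative: 0.7%, 3.2% and 4.8%. Afresh: 24%, 37% and 30%.

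**The case against.** The prose can be read to rescue the design. The RP2D criterion attaches to a dose level, not to a visit, and Section 5.6 ends dose finding once the RP2D is established with at least 6 treated. The ceiling of 22 equals 6 + 6 + 10, which fits cumulative counting far better than counting afresh. The percentages rest on assumed rates, and the background section expects largely non-overlapping toxicity. At 3/5/10% the difference is only about 0.3 points, and the 17.8 figure needs a 30% DLT rate at the starting level. Section 13.5 describes a trigger for DLT assessment, not a dose-assignment program, and its code is not shown.

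Much of this stands. A team reading the prose would probably stop correctly, and nothing shows that the trigger is miscoded. Cumulative counting is the better-supported reading. But it is an inference: no sentence overrides the instruction to go back to A and evaluate 3 patients. Nor does 3+3 convention fill the gap, because this version moves up on 0/3 only for the first cohort and otherwise requires 6, so a return to a half-filled level 1 is an ordinary path. The lettered steps are presented as the operative rules in two sections and should agree with the definition they are meant to deliver.

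**Conclusion.** The concern holds. As written, step B.1 contradicts the RP2D definition after any de-escalation that ends in a passing level. This is an error in the written rule whose intended correction is clear from the prose; it does not show that the trial would in fact loop. The counting rule is unstated, and the choice can lower the RP2D from level 1 to level 0 or to none. The size runs from about 3 to 18 percentage points of trials over the three tabulated scenarios and is smaller if DLTs are rarer. The example paths hold at any rates. The 6–22 range is incomplete under either reading, although with cumulative counts totals above 22 are uncommon (0.7–4.8% in these scenarios). It should be fixed.

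**What to change.** Amend Sections 5.6 and 13.1 in the same words:
- **B.1:** escalate only if level k+1 exists and has not been left for two or more DLTs; otherwise go to C with level k as the RP2D.
- **Counting:** DLT counts at a level are cumulative over all patients evaluated there. A return only completes the level to 6, and no further dose-finding patients are added if 6 have already been treated.

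In Section 13.2, restate the range as 6–28 and note that totals above 22 arise only on paths using all three levels. Reread the 36-month accrual statement at the same time: at 0.5–1 patient per month, 28 patients take 28 to 56 months, and 22 at the slower rate already take 22/0.5 = 44. Confirm that the trigger in Section 13.5 follows the corrected rule.

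The cost is a few lines of amendment text and one check of the trigger. The rule change adds no patients; the wider range only shows totals that the design can already reach.

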5.5 Definition of Dose-Limiting Toxicity

Dose-limiting toxicity (DLT) will be defined as any of the following events, detailed in Sections 5.5.2 and 5.5.3 that are possibly, probably or definitely attributable to protocol therapy. Decisions regarding the estimation of the recommended phase II dose and assigning treatment dosages to subsequent patients will be made on observations occurring in the first cycle of therapy.

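### The ten-patient expansion at the RP2D has no prespecified DLT boundary: no number of expansion DLTs requires a pause, DSMC review or reconsideration of the dose

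*Combined protocol and SAP*

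**What the plan says.** Section 13.1 sets the decision rule: "The RP2D is defined as the highest dose level in which there is no more than 1 DLT in 6 patients". It then states "Ten additional patients will be enrolled at the RP2D level". Section 5.6 says the same: "Once the RP2D is identified, an additional 10 patients will be enrolled at this dose level". Neither section makes the expansion depend on what is seen in it.

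The one rule that 13.1 gives for expansion patients is "Similar dose modifications as specified in Section 6 would be applied to these patients". Sections 6.1 and 6.2 deal with later cycles of the patient who had the toxicity. They do not deal with the starting dose of the next patient enrolled.

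Section 5.5 says that estimation of the RP2D and "assigning treatment dosages to subsequent patients will be made on observations occurring in the first cycle of therapy". Beyond the 3+3 steps it gives no count.

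Oversight is described in general terms:
- Section 5.5.1: DLTs are notified within 24 hours to the coordinating center and the Principal Investigators.
- Sections 7.4 and 12.7: SAEs go to the DSMC within 5 business days, with ongoing review and power to suspend or close.
- The monitoring plan in Section 12: monthly teleconferences while patients are active.
- Section 12.7: "The overall PI will provide a DSM report to the CU Cancer Center DSMC on a six monthly basis".
- Section 13.5: an automated trigger for DLT assessment, built on the escalation rules.

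On size and pace, Section 13.2 states "A total of 6 -22 adolescent and young adult subjects will be accrued into the trial" and "It is anticipated that 0.5-1 subjects will be accrued per month".

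**The concern.** The primary objective is to estimate the RP2D. Up to 16 patients will be treated at that dose, and 10 of them come after the dose has been fixed. The plan does not say what their first-cycle DLTs do to enrolment or to the RP2D. Followed as written, a dose with many expansion DLTs remains the RP2D, and each new patient still starts at it unless someone uses discretion.

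This matters because six patients are weak evidence about a DLT rate. A dose that passed by luck would show itself in the expansion, but no threshold tells the investigators or the DSMC when the early judgement has been contradicted.

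**Working it through.** **Inputs.** The acceptance rule (no more than 1 DLT in 6) and the expansion of 10 come from 5.6 and 13.1. Accrual of 0.5 to 1 per month comes from 13.2. The documents state no target or unacceptable DLT rate, so the true rate *p* is assumed over 10% to 50%.

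**1. The plan's own figure.** The upper end of the stated sample size is 22 = 6 + 6 + 10, that is, two levels of six plus a full expansion. The ten are counted as a fixed addition. (Longer paths through the written rules exist; that is a separate matter.)

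**2. Chance that a level passes once six are treated there.** P(X ≤ 1) = (1−p)^6 + 6p(1−p)^5.
- p = 0.30: 0.118 + 0.303 = 0.420
- p = 0.40: 0.047 + 0.187 = 0.233
- p = 0.50: 0.016 + 0.094 = 0.109

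**3. What six patients exclude (exact two-sided 95% upper limit).**
- 0/6: 1 − 0.025^(1/6) = 45.9%
- 1/6: the p that solves (1−p)^6 + 6p(1−p)^5 = 0.025, which is 64.1%
- For comparison, 1/16 gives 30.2%

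**4. What the expansion would show.** Expected DLTs among 10 are 10p, that is 3, 4 and 5 at 30%, 40% and 50%. P(at least 4 of 10) is 35.0%, 61.8% and 82.8%. Ten patients take 10/1 = 10 to 10/0.5 = 20 months.

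**5. Probability that the plan's rules force a pause on a DLT count.** Zero at every p. The 3+3 steps end at six patients, and the trigger in 13.5 follows those steps, so neither covers patients 7 to 16.

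**6. What a boundary could do (illustration only).** Pause for review if pooled DLTs at the dose exceed 1/3 of the patients treated there, checked after each patient from the ninth. This means 4 DLTs at 9–11 patients, 5 at 12–14 and 6 at 15–16. Start from 0 or 1 DLT in 6 with probabilities (1−p)^6/A and 6p(1−p)^5/A, where A is the acceptance probability in step 2. Add one Bernoulli(p) patient at a time and remove the paths that cross.

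At p = 0.40 the start is 0.20 on zero DLTs and 0.80 on one. The chance of crossing at patient 9 is 0.80 × 0.4³ = 0.051. At patients 10, 11, 13, 14 and 16 it is 0.097, 0.123, 0.052, 0.080 and 0.036. The total is 0.439. No path can first cross at 12 or 15, because the boundary rises by one there. Expected expansion enrolment is 10 − (7×0.051 + 6×0.097 + 5×0.123 + 3×0.052 + 2×0.080) = 8.1, and expected DLTs are 0.4 × 8.13 = 3.25 instead of 4.0.

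| True DLT rate (assumed) | Pause, given acceptance |
|---|---|
| 10% | 0.5% |
| 20% | 5.9% |
| 30% | 20.8% |
| 40% | 43.9% |
| 50% | 68.2% |

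The calculation treats each patient's cycle 1 as known before the next enrols. That is roughly right at 0.5 to 1 patient per month with 21-day cycles, and slightly optimistic for DLTs defined by a 14-day delay (21 + 14 = 35 days).

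**The case against.** The strongest reply is that the trial is small, slow and watched. The 24-hour DLT notice is not limited to the escalation phase. SAEs reach the DSMC within 5 business days, and it can suspend or close the trial. With one patient or fewer enrolled per month, people will see a run of DLTs. This stands, and it rules out three stronger readings:

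- *A toxic dose will run through the whole expansion.* Nothing in the plan forces that. What is true is that nothing in the plan requires otherwise.
- *The 3 to 6 patients enrolled between six-monthly reports are unmonitored.* The six-month interval belongs to the summary report, not to the first news of a serious event. Some haematologic DLTs might miss the SAE route, because 7.4.1 does not count most laboratory abnormalities as medical events. They still fall under the 24-hour notice, although that notice does not go to the DSMC.
- *The expansion data are ignored.* Section 13.4 includes all treated patients and summarises the DLT rate by dose level, so the rate at the RP2D will already pool them. The missing parts are the link to the RP2D decision and an interval.

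Two further points also stand. The 23% is conditional on a 40% level being tested in six patients; it is not the chance that the trial selects such a dose. If that level is level 2 and level 1 has an assumed 20% rate, level 2 is reached at first pass with probability 0.512 + 0.384 × 0.512 = 0.709, and reach-and-accept is 0.709 × 0.233 = 17%. With level 1 at 30% it is (0.343 + 0.441 × 0.343) × 0.233 = 12%. And the illustrative boundary is modest: it misses 56% of accepted 40% doses. The 1/3 is not in the documents and is twice the 1/6 tolerance that defines the RP2D, so it should not be read as the right threshold.

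What the reply does not supply is a number. Every safeguard it names is discretionary about DLTs.

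**Conclusion.** The concern holds in this form: the expansion has no prespecified DLT-based boundary, and the plan does not say whether its ten patients can change the RP2D. It does not hold as a claim that safety oversight is absent. The binomial results are exact given *p*; the values of *p* are assumptions, shown as a range. Between 30% and 50%, a level tested in six patients is accepted 42% to 11% of the time, so a contradicted RP2D is a realistic outcome to plan for. This should be corrected, but it does not invalidate the design.

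**What to change.** Amend 5.6 and 13.1 to say that:
- the RP2D is provisional until the expansion patients have completed cycle 1;
- first-cycle DLTs are pooled over the up to 16 patients at that dose;
- a cumulative boundary, chosen by the sponsor and given with its operating characteristics, pauses enrolment for DSMC review, and the text names who acts on it;
- the final RP2D statement takes account of all patients treated at that dose.

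Extend the trigger in 13.5 to patients 7 to 16. In 13.4, report the pooled DLT rate at the RP2D with an exact confidence interval.

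The cost is a short amendment and no added patients. With a boundary like the one illustrated, the chance of an unnecessary pause is about 6% at a true 20% rate and 0.5% at 10%. A stricter or looser boundary trades that against detection, which is why the operating characteristics belong in the plan.
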